**Effect of methotrexate carried by a lipid nanoemulsion
on left ventricular remodeling after
ST-elevation myocardial infarction**

NCT 03516903

October 13, 2020.

Statistical Analysis Plan

Study design: Prospective, double-blind, parallel arm, proof of concept, randomized controlled trial.

Study casuistic: 50 patients presenting with acute anterior wall STEMI, after proper reperfusion therapy and in stable clinical condition. Patients will be randomly assigned 1:1 to methotrexate carried by a lipid nanoemulsion (ddMTX-LDE) or matching placebo.

1. Study Population

The main population analysis of interest will be the *per protocol population*, that means, all patients who have been randomized and completed the 3 months follow-up with an adequate cardiac MRI with complete measurements of LV diastolic and systolic volumes and LVEF, and who have received at least one dose of the study drug. In an attempt to minimize bias for not doing an ITT analysis, baseline characteristics will be compared between both randomized arms within ITT and per protocol populations. Additionally, sensitivity analysis will be done including only patients who received the complete planned study doses of the investigational product.

2. Primary Endpoint

The primary endpoint of the study will be LV end-diastolic volume (LVEDV) assessed by cardiac MRI at 3 months. Both groups will be compared with a Student's t test or Wilcoxon rank sum test, as appropriate. Besides that, an analysis of variance (ANOVA) for repeated measures will be performed as sensitivity analysis in order to assess the serial measurements of LVEDV at baseline and at 3 months between both groups of interest, as well as comparison between groups regarding the difference between baseline and 3 months (delta). Mean difference between groups will be reported with corresponding 95% CI. If the variable does not follow a normal distribution, an alternative approach to estimate 95% CI will be used, like bootstrapping with 1,000 repetitions.

3. Safety endpoints

Both groups will be compared regarding the incidence of the following pre-specified adverse events of special interest: overall serious adverse events (SAE), as defined in the protocol; adverse events of special interest (AESI), namely, stomatitis, vomiting, diarrhea, cough with fever or dyspnea; and fatal or life threatening infections (defined as those ones needing vital organ support measurements, like mechanical ventilation or vasopressors, as a direct consequence of the infection, e.g., septic shock). In those outcomes, these variables will be compared as binary variables, with Chi square or exact test, as appropriate, with risk ratios (RR) and 95% CI reported according to Wald proportion tests.

Laboratory parameters will also be compared between groups, following same principles outlined for the primary endpoint. Parameters of interest will be: hemoglobin, white cell blood count, platelet count, liver transaminases (AST and ALT), total bilirubin, and creatinine. Since some of those tests are performed weekly, we will use a mixed linear model with study drug and week as fixed effect and patient as random effect. Least mean squares difference with corresponding 95% CI will be reported. Besides that, we also report percentage of patients with at least one change in security laboratory parameter as prespecified by study protocol.

4. Sample size calculation

Sample size was calculated considering an expected 20% decrease in LVEDV in the LDE-MTX group compared to placebo, based on cardiac MRI at 3 months. From a prior study (the METOCARD study^{1,2}), the expected mean LVEDV in the placebo arm is 197.6 mL with a common SD of 45.7 mL. For a two-tailed alpha of 5% and 80% power, we estimate our sample size as 21 patients per group. In order to account for eventual losses, we planned to enroll a total of 50 patients.

5. Interim analyses

The study had two pre-specified safety analysis (it was deemed to be stopped should any important imbalance, regardless of significance level, be found between safety outcomes). However, due to difficulty in enrolment after COVID-19 pandemic, a new unplanned efficacy interim analyses will be performed aiming to decide whether the study should be interrupted for futility or efficacy. For this third interim analysis, study will be stopped for efficacy if the experimental therapy is superior to the placebo group at a two-sided alpha of 0.05, regarding the primary endpoint, or if there is any difference favoring MTX for LVEF at an alpha = 0.05. Additionally, the study will be interrupted for futility if the conditional completion is < 30% for the primary endpoint and for LVEF.

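### The main LVEDV set is dosed patients with a complete 3-month MRI; no stated LVEDV analysis shows how far the result depends on patients without one

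*SAP*

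**What the plan says.** SAP Section 1 (Study Population) calls the main population per protocol. A randomised patient enters it after having "completed the 3 months follow-up with an adequate cardiac MRI with complete measurements of LV diastolic and systolic volumes and LVEF". A dosing condition is then added: "and who have received at least one dose of the study drug". Partial dosing excludes nobody, so this is in effect a dosed complete-case set.

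The same section acknowledges the departure from intention to treat and gives its answer: "In an attempt to minimize bias for not doing an ITT analysis, baseline characteristics will be compared between both randomized arms". That comparison is to be made "within ITT and per protocol populations", which is the only use the SAP makes of the ITT set.

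One further analysis is defined by population: "sensitivity analysis will be done including only patients who received the complete planned study doses of the investigational product".

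Section 2 (Primary Endpoint) adds that "an analysis of variance (ANOVA) for repeated measures will be performed as sensitivity analysis", together with a comparison of the change from baseline. Both alter the model, name no wider population and need both MRIs. The design line reads "Prospective, double-blind, parallel arm, proof of concept, randomized controlled trial". Section 4 plans 21 patients per group and enrols 50 to cover losses.

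**The concern.** Membership of the main set is decided after randomisation, by dosing and by obtaining a complete scan. If the reason a scan is missing is related to LVEDV, and this differs by arm, the comparison is no longer protected by randomisation. The SAP recognises the risk, but its remedy is descriptive. A baseline table can flag strong selection on ventricular size. It changes no estimate, and it carries no signal if loss follows what happened to the ventricle after baseline.

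The definition can also discard usable primary-endpoint data, namely an MRI from a never-dosed patient, or a scan that yields LVEDV but lacks systolic volume or LVEF. Neither exclusion is needed to analyse LVEDV.

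What is at stake is that a reader of the final result could not tell whether the LVEDV difference would survive plausible values for the patients without a scan.

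**Working it through.** **Plan's own figures (Section 4).** Target difference: 0.20 × 197.6 = 39.52 mL; SD 45.7 mL. By the normal approximation, n per group = 2 × (1.96 + 0.8416)² × (45.7 / 39.52)² = 2 × 7.849 × 1.337 = 20.99, so 21, as stated. Room for losses: 50 − 42 = 8 patients, or 16%. The sample size is not in question.

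**Assumptions not in the SAP.** 25 per arm, no true effect, SD 45.7 mL at both visits, baseline to 3-month correlation ρ of 0.5 or 0.8, and 4 patients lost from the active arm only. Loss follows a score whose correlation with its driver is q; moderate selection is q = 0.3 to 0.5. The 4 highest scores are lost.

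**Selection constant.** The four largest of 25 standard normal values have expectations 1.965, 1.524, 1.263 and 1.067, sum 5.819. The 21 retained patients therefore have mean score −5.819 / 21 = −0.277.

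**A. Loss follows the post-baseline residual.** Bias = 0.277 × q × √(1 − ρ²) × 45.7 mL, in favour of the active arm. Error is the two-sided rejection rate of the planned t test in 200,000 simulated trials per scenario.

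| ρ | q | Bias (mL) | Share of 39.52 mL | Error |
|---|---|---|---|---|
| 0.5 | 0.3 | 3.3 | 8% | 5.8% |
| 0.5 | 0.5 | 5.5 | 14% | 7.1% |
| 0.8 | 0.3 | 2.3 | 6% | 5.4% |
| 0.8 | 0.5 | 3.8 | 10% | 6.0% |

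The t test, the change-from-baseline analysis and a baseline-adjusted model share this bias, because the driver is unrelated to baseline. For the same reason, tests on baseline LVEDV reject at about 5%.

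**Milder split: 3 lost from active, 1 from placebo.** The constant becomes 4.752 / 22 − 1.965 / 24 = 0.216 − 0.082 = 0.134. Bias is 1.6 to 2.7 mL (ρ = 0.5) or 1.1 to 1.8 mL (ρ = 0.8), with error 5.2% to 5.8%.

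**B. Loss follows absolute 3-month LVEDV, 4 from active only, q = 0.3 to 0.5.**
- Planned t test, 0.277 × q × 45.7: 3.8 to 6.3 mL at either ρ.
- Planned change from baseline, multiply by (1 − ρ): 1.9 to 3.2 mL (ρ = 0.5) or 0.8 to 1.3 mL (ρ = 0.8).
- Baseline-adjusted model, multiply by (1 − ρ²): 2.8 to 4.7 mL or 1.4 to 2.3 mL.

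Here the planned change analysis is the least biased of the three. A test of baseline LVEDV in lost versus retained active patients rejects only 7% to 12% (ρ = 0.5) or 11% to 23% (ρ = 0.8) of the time.

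**C. Random loss, or the same selection in both arms.** Bias is 0. If the losses are in placebo instead, the sign reverses.

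**How likely is the lopsided split?** If 4 losses are unrelated to arm, all 4 fall in active with probability C(25,4) / C(50,4) = 12,650 / 230,300 = 5.5%. Exactly 3 do so with probability 2,300 × 25 / 230,300 = 25.0%.

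**The case against.** The departure from ITT is smaller than the label suggests. One dose suffices for inclusion, no reassignment of arms is described, and a 3-month MRI endpoint cannot be observed without the scan. What remains is mostly missing outcome data, which the protocol, not shown here, may address. The trial is a small, double-blind proof of concept with matching placebo, and the SAP states its limitation openly. The change-from-baseline analysis is a real partial safeguard, as B shows.

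Most of this stands, and it limits the weight of the point. It does not remove it. The choice of main set and the decision not to do an ITT analysis are made in this SAP. Blinding makes loss driven by knowledge of treatment less likely, but not loss through tolerability or clinical course. The change analysis offers nothing under A.

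Three stronger readings are tempting and unsupported:
- A reader might infer that the result will be biased in favour of methotrexate. The SAP gives no loss rate by arm, and the bias can be zero or of either sign.
- A reader might infer that measured LVEDV values will be thrown away. The definition permits this, but nothing shows that such patients exist.
- A reader might infer that analysing all randomised patients narrows the confidence interval. Imputing from arm and baseline essentially repeats a complete-case baseline-adjusted analysis. Any gain in precision comes from the covariate, which is a separate matter.

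**Conclusion.** The point holds as a moderate one: the plan should be changed, but nothing shows that its result will be wrong. Section 1 fixes a dosed complete-case set, concedes bias and answers it with a comparison that adjusts nothing. No stated LVEDV analysis shows how far the result depends on patients without an MRI.

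The figures of 2.3 to 5.5 mL and 5.4% to 7.1% error rest wholly on assumed correlations, moderate selection and a 4-versus-0 split, which chance alone would produce 5.5% of the time. The 3-versus-1 case is close to nominal. Perfect selection under A (q = 1) would give 7.6 to 11.0 mL, or 19% to 28% of the target, but that is an upper bound for this mechanism and should carry no weight in judging the plan.

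**What to change.** 1. Make the primary LVEDV analysis all randomised patients as assigned, using every observed 3-month LVEDV regardless of dosing and of whether systolic volume or LVEF is missing.
2. Report MRI non-completion by arm with reasons, and the baseline LVEDV of patients with and without the 3-month MRI, by arm.
3. Add one sensitivity analysis for missing MRIs: impute missing LVEDV from arm and baseline LVEDV, then shift the imputed values by arm, in either direction, until the conclusion changes. The shift is the essential part, since imputation alone leaves the bias in A untouched. With 4 of 25 imputed, a shift of d mL moves the arm mean by 0.16 × d, so offsetting 2.3 to 5.5 mL takes about 14 to 34 mL.
4. Keep the completer, full-dose, change-from-baseline and repeated-measures analyses as supportive.

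The cost is SAP wording and modest programming, with no new data. The effect is slightly diluted if some randomised patients were never dosed. No gain in precision should be claimed for this change.

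### The primary test of 3-month LVEDV is valid but gives up precision, because baseline LVEDV is used only in sensitivity analyses

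*SAP*

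**What the plan says.** Section 2 defines the outcome as a follow-up value: "The primary endpoint of the study will be LV end-diastolic volume (LVEDV) assessed by cardiac MRI at 3 months". The arms are compared by a Student's t "test or Wilcoxon rank sum test, as appropriate". Baseline LVEDV appears only afterwards. A repeated-measures ANOVA is planned as a sensitivity analysis "in order to assess the serial measurements of LVEDV at baseline and at 3 months between both groups of interest", together with a between-arm comparison of the change from baseline. No analysis in the SAP uses baseline LVEDV as a covariate.

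Section 4 sizes the trial on the same unadjusted comparison: "the expected mean LVEDV in the placebo arm is 197.6 mL with a common SD of 45.7 mL", a 20% reduction, two-sided 5%, 80% power and 21 per group, with 50 enrolled to allow for losses. No correlation between baseline and 3 months is given.

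Section 5 adds an unplanned efficacy look "due to difficulty in enrolment after COVID-19 pandemic". Efficacy stopping requires the treatment to be "superior to the placebo group at a two-sided alpha of 0.05, regarding the primary endpoint", with LVEF as an alternative route. The futility rule also refers to the primary endpoint.

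**The concern.** Baseline LVEDV is likely to predict 3-month LVEDV in the same patient. An unadjusted test leaves that predictable variation in the error term, where it widens the interval and lowers power.

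The sensitivity analyses do not recover the loss. They do not decide the primary result. With only two time points, the group-by-time term of the repeated-measures ANOVA is the change-score comparison, so the plan has one alternative analysis and not two. A change score fixes the baseline coefficient at 1 instead of estimating it, which is inefficient when the correlation is modest.

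The consequence is larger here than in a big trial. About 21 evaluable patients per arm are expected, recruitment is slow, and the unadjusted comparison appears to feed the efficacy and futility decisions in section 5. A wide interval also makes a null or borderline result hard to interpret.

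**Working it through.** **Inputs from SAP section 4:** placebo mean 197.6 mL, common SD 45.7 mL, 20% effect, two-sided alpha 0.05, 21 per arm. The effect is 0.20 × 197.6 = 39.52 mL, or 39.52/45.7 = 0.865 SD.

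**Assumed:** the baseline to 3-month correlation r, shown over a range. For the change score, baseline SD is also taken as 45.7 mL.

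**The plan's own figure.** n = 2(1.960 + 0.842)²/0.865² = 21 per arm by the normal approximation, so the stated size reproduces. By the noncentral t (40 df), 21 per arm gives 78.1% power and 22 are needed for 80%.

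**Formulas.**
- Unadjusted: SE = 45.7 × √(2/21) = 14.1 mL, 40 df.
- ANCOVA: residual SD = 45.7 × √(1 − r²), 39 df.
- Change score: SD = 45.7 × √(2(1 − r)), 40 df.

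| Analysis, 21 per arm | Power, 20% effect: formula | Same, simulated | Power, 15% effect (29.64 mL) | 95% CI half-width, mL | Power of change score, 20% effect |
|---|---|---|---|---|---|
| Unadjusted | 78.1% | – | 53.6% | 28.5 | – |
| ANCOVA, r = 0.3 | 81.7% | 80.6% | 57.5% | 27.2 | 63.7% |
| ANCOVA, r = 0.5 | 88.4% | 87.7% | 65.8% | 24.7 | 78.1% |
| ANCOVA, r = 0.7 | 96.9% | 96.3% | 81.9% | 20.4 | 94.2% |
| ANCOVA, r = 0.8 | 99.5% | 99.4% | 92.7% | 17.1 | 99.1% |

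The simulation (20,000 trials) includes the cost of chance baseline imbalance, which the formula ignores; the formula is high by about 1 point at most. At r = 0.2 the formula gives 79.6% and the simulation 78.5%, in effect no gain. At r = 0 simulated ANCOVA power is 77.2%, a cost of about 1 point.

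**Type I error.** In a separate simulation (40,000 trials) both tests hold their level: 5.2% and 4.9% for the t test, and 5.1% and 4.9% for ANCOVA, at r = 0.5 and 0.7.

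**Equivalent sample size.** 21/(1 − r²) = 23.1, 28.0 and 41.2 per arm at r = 0.3, 0.5 and 0.7. The simulated powers at r = 0.3 and 0.5 correspond to slightly fewer, about 22 and 27.

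**The same loss seen conditionally.** If baseline SD is 45.7 mL, a one-SE chance difference at baseline is 14.1 mL. It moves the unadjusted 3-month difference by about r × 14.1 = 4.2, 7.1 or 11.3 mL at r = 0.3, 0.5 or 0.8. This is not a second harm.

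**At the interim look.** The SAP gives no sample size for it. Assuming 15 per arm for illustration, power is 63% unadjusted, against 75% (r = 0.5) or 89% (r = 0.7) with ANCOVA.

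**The case against.** The strongest reply is that nothing is wrong. Endpoint, test and sample size agree with each other, the test is valid, and this is a proof-of-concept trial. Baseline is not ignored, since change is analysed and baseline characteristics are compared by arm. On this view, ANCOVA is a reviewer's preference. It stands that the plan contains no error here. But the choice is fully specified, it is less efficient than an alternative that uses data already collected, and it can still be changed cleanly.

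Two technical objections are correct and limit the claim:

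- The change score is less precise than the raw 3-month value below r = 0.5 only if the two SDs are equal. In general the threshold is r = SD(baseline)/(2 × SD(3 months)). If baseline SD were 0.8 times the 3-month SD, the threshold would be 0.4 and change-score power at r = 0.5 would be 85%, not 78%. ANCOVA power does not depend on the baseline SD and remains 88%.
- The benefit depends on r, which the SAP does not give. At r = 0.3 the simulated gain is about 2.5 points. If all 50 enrolled patients were evaluable (25 per arm), unadjusted power would already be 85%.

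The LVEF route to stopping is also untouched by adjusting LVEDV.

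**Conclusion.** The concern holds as a loss of precision, not as bias or an invalid test. The direction is firm: at 21 per arm ANCOVA costs about 1 point of power if baseline is uninformative, and gains about 10 points at r = 0.5 and 18 at r = 0.7 (simulated, against 78.1%). The variance of the treatment estimate falls by about r², which is 9%, 25% and 49% at r = 0.3, 0.5 and 0.7.

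The size rests on the SAP's SD of 45.7 mL, on 21 evaluable patients per arm, and on an assumed r. That the baseline measurement is by MRI is inferred from the endpoint definition and the serial comparison. The per-protocol population, the open choice between t test and Wilcoxon, and the interim alpha are separate matters. The change should be made, but the plan is not invalid without it.

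**What to change.** Before the interim data are unblinded, amend sections 2 and 5:

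1. Make the primary analysis an ANCOVA of 3-month LVEDV on treatment arm and baseline LVEDV. Take the adjusted mean difference, 95% CI and p-value from that one model.
2. Use the same model wherever section 5 refers to the primary endpoint.
3. If residuals are clearly non-normal, take the CI and p-value from one procedure applied to the adjusted difference, for example a permutation test and the interval obtained by inverting it.
4. State a rule for a missing or inadequate baseline scan. Section 1 requires that patients "completed the 3 months follow-up with an adequate cardiac MRI with complete measurements of LV diastolic and systolic volumes and LVEF", which does not clearly cover baseline. Imputing the overall baseline mean, pooled over arms, is one option.
5. Keep the unadjusted t test or Wilcoxon and the change comparison as sensitivity analyses.

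The cost is SAP wording, one degree of freedom and the missing-baseline rule; no new patients or measurements are needed. With 10% of baselines missing at random and mean-imputed, simulated type I error stays at about 5% (4.8%, 5.1% and 5.0% at r = 0.3, 0.5 and 0.7). Power at r = 0.5 falls from about 88% to about 86%. If the change were made after unblinding, it would be open to the charge of being data-driven.

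### The repeated-measures ANOVA planned as the LVEDV sensitivity analysis names no treatment contrast; its two standard arm terms give a half-size effect or repeat the delta comparison

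*SAP*

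**What the plan says.** SAP section 2 fixes a single-visit primary endpoint: "The primary endpoint of the study will be LV end-diastolic volume (LVEDV) assessed by cardiac MRI at 3 months". The primary test is unadjusted: "Both groups will be compared with a Student's t test or Wilcoxon rank sum test, as appropriate".

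The section then adds that "an analysis of variance (ANOVA) for repeated measures will be performed as sensitivity analysis in order to assess the serial measurements of LVEDV". Two visits enter this analysis, the pre-treatment one and the 3-month one, and the arms are to be compared. The same sentence goes on: "as well as comparison between groups regarding the difference between baseline and 3 months (delta". It does not say whether the treatment comparison is the group main effect, the group-by-time term or a contrast at one visit. No baseline-adjusted analysis of LVEDV is named.

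SAP section 4 gives the planned effect: "Sample size was calculated considering an expected 20% decrease in LVEDV in the LDE-MTX group compared to placebo", with a placebo mean of 197.6 mL, a common SD of 45.7 mL and 21 patients per group.

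**The concern.** A sensitivity analysis should show whether the LVEDV answer survives a reasonable change of method. With two arms, one visit before treatment and one after, the repeated-measures ANOVA table has only two terms that involve arm, and neither does that job well.

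- **Group main effect.** This compares each patient's average of the two visits. Randomization makes the expected baseline difference zero, so the term estimates the average of zero and the drug effect.
- **Group-by-time.** This is the comparison of change from baseline, which the same sentence already lists.

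If the group line is reported, a true benefit of the planned size would appear at half size beside the primary estimate, usually without significance, and could be misread as fragility. If the interaction is reported beside the delta result, one result may pass for two that agree. Because no term is named, the choice could also be made after the results are seen.

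**Working it through.** **Inputs.** From SAP section 4: effect 0.20 × 197.6 = 39.52 mL, SD 45.7 mL, two-sided alpha 5%, 21 per arm, 50 enrolled (25 per arm at 1:1). Assumed, because the SAP gives no values: the same SD at baseline, normal data, and a correlation r between baseline and 3 months of 0.3 to 0.8.

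**1. The plan's own figure.** n = 2 × (1.960 + 0.842)² × 45.7² / 39.52² = 20.99, so 21 per arm. The stated figure reproduces. By the noncentral t distribution, the primary t test has 78.1% power at 21 per arm and 85.0% at 25.

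**2. What each analysis estimates.**
- Group main effect: expected difference (0 + 39.52)/2 = 19.76 mL; SD of a patient's two-visit mean = 45.7 × √((1 + r)/2).
- Group-by-time, or delta: expected difference 39.52 mL; SD of change = 45.7 × √(2(1 − r)).
- ANCOVA of 3-month LVEDV on baseline: expected difference 39.52 mL; residual SD = 45.7 × √(1 − r²).

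**3. Worked case, r = 0.5, 21 per arm.** √(2/21) = 0.3086.
- Group: SD 39.58; noncentrality 19.76/(39.58 × 0.3086) = 1.62; power 35%.
- Delta: SD 45.7; noncentrality 39.52/(45.7 × 0.3086) = 2.80; power 78%.
- ANCOVA: SD 39.58; noncentrality 39.52/(39.58 × 0.3086) = 3.24; power 88%.

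**4. Range.** The primary test does not depend on r.

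| r | Group, 21/arm | Delta, 21/arm | ANCOVA, 21/arm | Group, 25/arm |
|---|---|---|---|---|
| 0.3 | 40% | 64% | 82% | 46% |
| 0.5 | 35% | 78% | 88% | 41% |
| 0.7 | 32% | 94% | 97% | 37% |
| 0.8 | 30% | 99% | 99.5% | 35% |

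The ANCOVA column is slightly optimistic, because it keeps 40 degrees of freedom and ignores the cost of estimating the slope. The group term would need about 55 (r = 0.3) to 76 (r = 0.8) patients per arm for 80% power.

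**5. Simulation, 20,000 trials, r = 0.7, 21 per arm.** Mean estimates were 19.76 mL for the group term and 39.56 mL for delta. Rejection rates were 32% (group), 94% (delta) and 78% (primary). With no drug effect the group term rejected in 4.9%, so its type I error holds.

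**6. Agreement with the primary test.** In simulations over r = 0.3 to 0.8, when the primary test was significant the group term was not in about 50 to 62% of trials at 21 per arm, and in about 47 to 58% at 25 per arm.

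**7. Identities.** Sums of squares on one simulated data set gave interaction F = 30.955, equal to the squared t of the delta test, and group F = 3.231, equal to the squared t on two-visit means. The interaction identity is with a t test on delta; a rank test on delta would not match it numerically.

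**The case against.** The strongest reply is that the SAP never says the group main effect is the treatment comparison. Averaging the two visits is a poor way to assess serial measurements, so the wording fits a group-by-time analysis at least as well. The delta clause can also be read as a second purpose of the same ANOVA, which makes delta its interaction contrast. On that reading nothing is diluted and nothing is counted twice. This stands. A reader might infer that the planned ANOVA halves the drug effect, but the text supports that only if the group line is what gets reported. The laboratory model in section 3 has drug and week effects and no drug-by-week term, which shows a visit-averaged arm contrast used elsewhere in the SAP; it does not settle what was meant for LVEDV.

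A third use is a 3-month contrast taken from within the ANOVA. It estimates the full effect, so the two standard terms are not the only possibilities. With both visits complete, however, its point estimate is the raw difference in 3-month means, which is the primary estimate again.

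A reader might also infer that the group term is invalid. It is not: it keeps its 5% error rate, and its faults are a different target and low power. Nor does the plan lack a full-effect sensitivity analysis, since the delta comparison is one, with 64 to 99% power over the assumed correlations.

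Finally, no decision hangs on this ANOVA. The stopping rules in section 5 use the primary endpoint and LVEF, and the sample size rests on LVEDV at 3 months. This stands and limits the importance of the point. It does not remove it, because none of the readings supplies a baseline-adjusted estimate of the 3-month difference.

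**Conclusion.** The point holds as a modest fault in the choice and wording of a sensitivity analysis. The treatment contrast is not named. Of the two standard arm terms, one estimates 19.8 mL of a planned 39.5 mL with about 30 to 40% power at 21 per arm, against 78% for the primary test; the other repeats delta and adds no further check.

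The halving follows from randomization and two visits and needs no assumed correlation. The power figures rest on the planned effect, normal data, equal SDs and a correlation of 0.3 to 0.8. The case for change does not depend on guessing which term was intended: ANCOVA uses a baseline already collected, targets the full 3-month difference, and has about 82 to 99% power over the same range, against 64 to 99% for delta.

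**What to change.** In SAP section 2:

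1. Replace the repeated-measures ANOVA with a baseline-adjusted sensitivity analysis of 3-month LVEDV: ANCOVA with arm and baseline LVEDV, or the equivalent two-visit model with the arms constrained equal at baseline.
2. Report the adjusted between-arm difference at 3 months with its 95% CI.
3. Report the delta comparison once, and not again as an ANOVA interaction.
4. State that an arm effect averaged over baseline and 3 months is not a treatment estimate.

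If the ANOVA is kept, the least that is needed is a clause naming the contrast that carries the treatment comparison; that removes the ambiguity but adds no new check.

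The cost is a small change of SAP wording and a linear-adjustment assumption confined to a sensitivity analysis. No new data or patients are needed, and the primary test does not change.

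### If LVEDV is judged non-normal, the primary p-value and its 95% CI come from methods that address different effects and can disagree; both should come from one method

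*SAP*

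**What the plan says.** Section 2 (Primary Endpoint) of the SAP contains three statements that have to be read together.

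- The test: "Both groups will be compared with a Student's t test or Wilcoxon rank sum test, as appropriate". No criterion for the choice is given.
- The effect measure, stated without condition: "Mean difference between groups will be reported with corresponding 95% CI".
- The fallback when the variable is not normal: "an alternative approach to estimate 95% CI will be used, like bootstrapping with 1,000 repetitions". Bootstrapping is offered as an example, and no type (percentile, BCa, studentised) is named.

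The non-normal branch therefore changes the test and the way the interval is computed, but not the effect being estimated. No rank-based estimate is mentioned. Section 3 applies the same principles to the laboratory parameters. Section 5 allows stopping for efficacy at a two-sided 0.05 on the primary endpoint.

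**The concern.** The Wilcoxon test asks whether values in one arm tend to exceed those in the other. It is not a test of the mean difference. An interval for the mean difference, by bootstrap or otherwise, answers the other question. With skewed or heavy-tailed data the two can part: p below 0.05 with an interval that includes zero, or the reverse. The SAP gives no rule for that case, so the primary result could be worded either way.

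A second, smaller issue concerns the fallback itself. The simple percentile bootstrap runs narrow in small samples. If that form were chosen, the interval meant to protect against non-normality would usually cover the true difference less often than the t interval it replaces.

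**Working it through.** **Inputs from the SAP, section 4.** Placebo mean 197.6 mL, common SD 45.7 mL, a 20% reduction, two-sided alpha 5%, power 80%, 21 per group.

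**The plan's own figure.** The planned difference is 0.20 × 197.6 = 39.52 mL. The normal-approximation sample size is 2 × (1.960 + 0.842)² × (45.7/39.52)² = 20.99, so 21 per group. The stated size is reproduced and this point does not affect it.

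**Assumptions.** The SAP gives no distribution for LVEDV, so the shapes are assumed. Its coefficient of variation is 45.7/197.6 = 0.231. A lognormal with that value has log-SD √ln(1 + 0.231²) = 0.23, taken as the mild case. A log-SD of 0.6 is the more skewed case and has no support in the SAP. Data were rescaled to SD 45.7 mL. A trial was flagged non-normal if Shapiro-Wilk gave p < 0.05 in either arm. The bootstrap was the percentile form with 1,000 resamples.

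**Disagreement between rank-sum p < 0.05 and a percentile interval that excludes zero, 21 per arm, among flagged trials**

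| True difference | Disagree |
|---|---|
| 0 | 4-5% |
| 39.5 mL | 9-14% |

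**As a share of all trials.** In the mild case about 31% of trials are flagged. At 39.5 mL, 8.5% of those disagree: 0.31 × 8.5% ≈ 2.6% of all trials (2.7% from unrounded counts). With no effect the share is 1.3%, and with normal data about 1% or less. At log-SD 0.6 most trials are flagged, so the share of all trials is close to the flagged share.

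**Where the disagreement comes from.** Replacing the bootstrap by the ordinary t interval does not remove it. With exponential data at 39.5 mL (all trials), rank test and percentile interval disagree in 12.9%, rank test and t interval in 14.3%. With a t distribution on 3 df the figures are 11.2% and 12.4%. The cause is the mismatch of rank test and mean.

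**Coverage with similar spread.** For a percentile interval the half-width is roughly 1.960 × √(20/21) × SE; for the t interval with 40 df it is 2.021 × SE. The ratio is 1.960 × 0.976/2.021 = 0.946. In mL: SE = 45.7 × √(2/21) = 14.10; the t half-width is 2.021 × 14.10 = 28.5; the percentile half-width is 0.946 × 28.5 = 27.0. Simulated coverage with skewed data was 92.7-93.9% for the percentile interval and 94.6-96.3% for the t interval.

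**Coverage with unequal spread.** With the SD twice as large in the smaller arm (17 against 25):

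| Shape | Percentile | Pooled t | Welch |
|---|---|---|---|
| Exponential | 91.6% | 91.2% | 93.7% |
| Normal | 92.8% | 91.9% | 94.9% |

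Welch stayed at 93.7-96.0% in every scenario where it was run.

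**The case against.** - **The pairing is inferred.** The SAP does not expressly tie the Wilcoxon test to the bootstrap interval. That stands, but both are triggered by non-normality and the mean difference is kept throughout, so it is the natural reading.
- **The test decides and the interval only describes.** Section 2 says the groups are compared by the named test, and the stopping rule in section 5 is set in terms of alpha. This is reasonable, but the SAP does not say it, and a primary result whose interval contradicts its p-value is still hard to report.
- **Conflict is not frequent.** A reader might infer that the two methods often disagree. The documents do not support that: at the SAP's own spread the share is a few percent of all trials, and larger figures need a skew the SAP does not suggest.
- **The bootstrap is not always inferior.** A reader might infer that the fallback interval is simply worse than the t interval. The SAP names no bootstrap type and offers bootstrapping only as an example. With unequal spread and arm sizes, the percentile form slightly beat the pooled t. The loss of coverage is conditional.
- **Type I error.** A reader might infer that choosing the test after a normality check inflates it materially. Simulated type I error of that two-stage choice was 4.7-5.5%, so it does not.

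**Conclusion.** The point holds as a matter of coherence. In the non-normal branch, as naturally read, the primary p-value and interval address different effects, can disagree about significance, and have no rule of precedence. The size is about 9-14% of flagged trials at 39.5 mL and 4-5% with no effect, under assumed lognormal shapes and a Shapiro-Wilk flag. It is about 3% of all trials at 39.5 mL if skew is as mild as the SAP's own mean and SD suggest.

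Separately, and only if the bootstrap is the percentile form, coverage is usually about 1-3 points below the t interval at 21 per arm with similar spread (about 93-94% against 95-96%). Neither issue touches the sample size. This should be corrected because it concerns the primary endpoint and is cheap to settle, not because the primary inference is badly damaged.

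**What to change.** State in section 2 that the primary p-value and 95% CI come from the same method, and that this result decides. Either option works:

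1. The Welch t test, or a linear model adjusted for baseline LVEDV, with its own interval for the mean difference, whatever the normality check shows. This keeps the effect on which the sample size was based.
2. If the Wilcoxon test is used, the Hodges-Lehmann shift with the interval obtained by inverting that test, plus a criterion for when this branch applies.

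Changing only the interval, whether to the t form or to another bootstrap, would leave the mismatch in place. Make the change before the efficacy interim analysis in section 5, and carry it to any laboratory comparison that follows the same principles.

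The cost is a sentence in the SAP and a line of code. The downside of option 2 is that the Hodges-Lehmann shift is not a mean difference, so the results table needs a footnote.
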